4.1.2 Secondary endpoints

- Evolution of daily extravascular lung water index (EVLWi), cardiac index, global end-diastolic volume index, pulmonary vascular permeability index, measured by transpulmonary thermodilution during 7 days.
- Overall survival at 30 days
- Mortality rate in ICU, in hospital
- Rate of withdraw or withhold life-sustaining treatments decision at Day 30
- Vascular leak:
 - Daily weight until D7 (% of D1)
 - Daily fluid balance until D7
 - Evolution of albuminemia until D7
- Pulmonary recovery:
 - Duration of mechanical ventilation (MV) and MV free days at D30
 - Ventilator-free survival (proportion of participants alive and off invasive mechanical ventilation) at D30
 - PaO₂/FiO₂ and Murray ARDS severity score over 15 days
 - Evolution of pulmonary SOFA score over 15 days
 - Evolution of radiological Weinberg score over 30 days, analysed by a specialized radiologist, blinded for the treatment group
 - Rate of rescue therapy with VV-ECMO
- Evolution of daily sequential organ failure score (SOFA) and organ failure (one or more SOFA sub-score ≥3) failure free days at D15
- Hemodynamic parameters
 - systolic, diastolic, mean blood pressure, heart rate twice a day during 7 days
 - lactate clearance, measured once a day during 7 days
 - catecholamine-free days at D30
- Duration of renal replacement therapy (RRT), and RRT free days at D30
- Nature and frequency of adverse events
- Evolution of FX06 concentration from H0 to H1, measured at time 0 (before FX06 application) and after 5, 15, 30, 60 min
- PK/PD analysis will be performed from those dosages, with a reduction of EVLWi of more than 30% before and 3 hours after injection as primary PD endpoint at day 2
- Immunogenicity of the drug will be tested at day 7, according to manufacturer's procedure (cf 5.7)

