12 STATISTICAL ASPECTS

12.1 Description of statistical methods to be used including the timetable for the planned interim analyses

The statistical analysis will be performed by a biostatistician of the Clinical Research Unit of Pitié-Salpêtrière Hospital, under the responsibility of [name] [name].

Statistical analyses will be performed with the SAS® or R software with the most recent version at the time of the analysis.

Descriptive analysis will always be overall and by treatment group.

Unless specially mentioned, comparative analysis between groups will be systematically performed without adjustment (univariate analysis);

Flow chart

A flow chart according to the CONSORT recommendations will describe the recruitment and the follow-up of all study population.

Study population

The primary analysis of efficacy endpoints will be performed on all randomized patients for whom a baseline evaluation is available, on an intention-to-treat (ITT) population. All patients will therefore be analyzed in their initial randomization groups.

The safety set is defined as all randomized patients having received at least one dose of study treatment. Safety endpoints will be analyzed on the safety set.

Descriptive analysis

Qualitative variables will be described with frequency and percentage distributions, and quantitative variables with median, interquartile range, minimum and maximum values, mean and standard deviation.

Censored data will be described by Kaplan-Meier estimation or cumulative incidence function, with rate at D7 and D30 with 95% confidence interval.

Baseline characteristics

Demographical, clinical, biological and treatment characteristics will be described.

Primary analysis

The primary analysis will be performed in the intention to treat population.

The primary outcome is the change in EVLWi between D1 and day 7. These changes will be compared between both arms using analysis of covariance (ANCOVA), adjusted for the D1 EVLWi. This is fully equivalent to comparing EVLWi scores at D7 adjusted for the baseline EVLWi. Results will be expressed in terms of adjusted mean changes, with their 95% confidence interval. The unadjusted supportive analysis will be carried out by comparing EVLWi at day 7 between the two arms with a t test.

If the distribution of EVLWi is clearly incompatible with the ANCOVA or t test assumptions, then these analyses will be conducted on the ranks.

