For patients dying before 7 days, the last thermodilution data will be retained for the primary analyses. If the patient's condition no longer warrants the presence of the transpulmonary thermodilution systems, then the catheter is removed before 7 days. In this case, the measurement of EVLWi can no longer be made, the last thermodilution data will be retained for the primary analyses. A sensitivity excluding those patients will be performed for analysing the primary endpoint.

Secondary analyses

For safety, the types and severity of AEs and SAEs will be described as frequency and percent by treatment arm. Fisher's exact tests will be used to compare the two treatment arms in terms of proportion of patients with death (all cause), at least one AE/SAE, at least one SAE. The number of these events (except death) will be compared between arms by Poisson regression.

Overall survival at D30 will be compared between the two groups using a logrank test.

The evolution of EVLWi during 7 days and other longitudinal repeated efficacy secondary outcomes will be compared between the two groups using a linear mixed effect model to take into account within subject correlation. If the model assumptions (normally distributed residuals with constant variance) is debatable, these analyses will be conducted on the ranks.

For other efficacy secondary outcomes, data will be described graphically and compared between arms by:

- chi2 test or fisher test for binary outcomes;
t-test or wilcoxon rank-sum test for quantitative variables.

Subgroups analyses will be performed according to :

- Presence of VV-ECMO at baseline (Yes/No)
- EVLWi at baseline (>10 ml/kg) (Yes/ No)

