12.2 Calculation hypotheses for the number of participants required and the result

According to previous studies, standard deviation for EVLWi during ARDS is around 5 ml/kg predicted body weight [2]. Assuming a baseline mean of EVLWi of 13.4 and a 30% decrease in EVLWi in FX06 treated patients compared to controls at Day 7, **for 80% power and an overall 5% two-sided α -risk**, the required sample size is **25 patients per group**.

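### Lactate clearance has no formula and would be compared without D1 adjustment; log lactate adjusted for log D1 would be a cheap, more efficient replacement (minor)

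*Protocol*

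**What the plan says.** Protocol section 4.1.2 lists, under hemodynamic parameters, "lactate clearance, measured once a day during 7 days". The Summary repeats the item. Both the Summary and section 3.2 name lactate clearance among the measures of the vascular (capillary) leak objective. No formula and no reference time are given anywhere. Weight, in the same list, does have its reference stated: "Daily weight until D7 (% of D1".

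Three statements in section 12.1 govern the analysis:

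- General default: "Unless specially mentioned, comparative analysis between groups will be systematically performed without adjustment (univariate analysis".
- Repeated secondary outcomes, which include daily lactate clearance: "compared between the two groups using a linear mixed effect model to take into account within subject correlation". No baseline covariate is named.
- Fallback: "If the model assumptions (normally distributed residuals with constant variance) is debatable, these analyses will be conducted on the ranks".

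Baseline adjustment is written in for the primary endpoint only, which is compared "using analysis of covariance (ANCOVA), adjusted for the D1 EVLWi".

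The inclusion criteria in section 6.1 require ARDS and mechanical ventilation. None requires shock or a raised lactate.

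**The concern.** Clearance in its usual sense divides the fall in lactate by the patient's own D1 value. When that value is near normal, the denominator is small and noisy. A patient who goes from 1.0 to 1.5 mmol/L scores −50%, one who goes from 4.0 to 2.0 mmol/L scores +50%, and the two cancel in a mean. The score is skewed and its variance depends on D1, which sits badly with the normal, constant-variance residuals that section 12.1 asks for.

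The unadjusted default adds to this. A change score without its baseline as covariate is inefficient whenever the correlation between D1 and follow-up is modest. With 25 patients per arm, a real difference in lactate could be missed on an endpoint tied to the leak objective, although the same measurements could be analysed more efficiently.

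**Working it through.** **The plan's own figure.** Section 12.2 powers only the primary endpoint. It takes a "standard deviation for EVLWi during ARDS is around 5 ml/kg predicted body weight", a baseline mean of 13.4 and a 30% decrease.

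- Difference: 0.30 × 13.4 = 4.02 ml/kg.
- n per arm = 2 × (1.960 + 0.842)² × 5² / 4.02² ≈ 24.3, rounded up to 25.
- Power at 25 per arm: 81.1% (normal approximation) or 79.5% (t distribution).

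The stated 25 per group reproduces. No power is stated for lactate.

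**Inputs for lactate.** From the protocol: 25 per arm, 1:1 allocation, two-sided 5%. Everything else is assumed, because the protocol gives no lactate figures: clearance = (D1 − Dn)/D1; D1 and follow-up lactate lognormal with median 1.5 mmol/L and log-SD 0.45; FX06/placebo ratio 0.70; correlation between log D1 and log follow-up of 0.2, 0.4 or 0.6; one follow-up day, not the full mixed model. Power is the share of simulated trials with p < 0.05.

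**Shape of the ratio.** At correlation 0.4 the SD of clearance is about 0.69 in the lowest third of D1 values and 0.37 in the highest third. Constant variance would therefore fail under these assumptions.

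**Power at correlation 0.2 / 0.4 / 0.6**

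| Analysis | Power (%) | Loss against last row (points) |
|---|---|---|
| Clearance, unadjusted (section 12.1 as written) | 53 / 66 / 84 | 27 / 18 / 8 |
| Clearance on ranks, unadjusted (section 12.1 fallback) | 56 / 69 / 85 | 24 / 15 / 7 |
| Clearance with D1 covariate | 66 / 76 / 89 | 14 / 8 / 3 |
| Raw lactate with D1 covariate | 75 / 79 / 88 | 5 / 5 / 4 |
| Ranked clearance with ranked D1 covariate | 76 / 81 / 90 | 4 / 3 / 2 |
| Log lactate with log D1 covariate | 80 / 84 / 92 | – |

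**Where the loss comes from.** Differences between rows split the 27 / 18 / 8 points into three steps:

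- Adding D1 as covariate to clearance: 66 − 53, 76 − 66, 89 − 84 = 13 / 10 / 5.
- Replacing the ratio by the raw level, both adjusted: 75 − 66, 79 − 76, 88 − 89 = 9 / 3 / −1.
- Taking logs: 80 − 75, 84 − 79, 92 − 88 = 5 / 5 / 4.

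The missing D1 adjustment is the largest step throughout. The ratio form matters mainly at low correlation. Once lactate is on the log scale with log D1 as covariate, the ratio and the level give exactly the same test.

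**Sensitivity.** At correlation 0.75 every analysis in the table has 96% power or more, and the plan as written loses only about 2 points. A second set of simulations fixed the effect so that the ideal baseline-adjusted analysis had about 80% power. Unadjusted clearance then had 49–70% with lognormal lactate (log-SD 0.3–0.6) and 43–71% with normal lactate floored at 0.4 mmol/L. Ranked clearance adjusted for ranked D1 had 76–78% and 74–77%.

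**The case against.** The strongest objection is that the scenario is assumed. The protocol does not define clearance as a ratio to D1; it writes a percentage of D1 for weight but not for lactate. It gives no lactate level, spread, correlation or effect. A lognormal model makes the log analysis the best one by construction, and one day stands in for seven. This stands: the figures show a plausible size and are not estimates for this trial. The normal-lactate scenarios show that the loss from unadjusted clearance does not depend on the lognormal choice.

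A second objection is that formulas, transformations and covariates are often left to a statistical analysis plan, which is not at hand. That is fair for the formula. The protocol does, however, fix the named endpoint and the unadjusted default, and these two together produce most of the loss.

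A reader might infer something stronger: that dividing by D1 ruins the endpoint even when D1 is adjusted for, or that ranking cannot rescue it. The calculations do not support this. Adjustment recovers much of the loss, and ranked clearance with ranked D1 comes within 2–4 points of the log analysis. The 14 / 8 / 3 points that adjusted clearance still loses cannot all be charged to the ratio either, since about 5 / 5 / 4 points come from taking logs. What remains is that section 12.1 names no D1 covariate for this endpoint, on ranks or otherwise.

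**Conclusion.** The point holds as a minor, inexpensive improvement. As written, lactate clearance is undefined and, in its usual sense, would be analysed as an unadjusted ratio to D1. Under the stated assumptions this costs roughly 27 / 18 / 8 points of power at D1 correlation 0.2 / 0.4 / 0.6 against log lactate adjusted for log D1, and about 2 points at 0.75. The largest part is due to the missing baseline adjustment. The size rests on the assumed formula, near-normal D1 lactate, the lognormal distribution, the ratio of 0.70 and a single follow-up day. This is one secondary endpoint among many with no power claimed for it, so it gives no reason to doubt the primary analysis or the sample size.

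**What to change.** In section 4.1.2, the Summary (objective and endpoint) and the objective in section 3.2, replace lactate clearance by daily arterial lactate to D7, so that objective and endpoint still agree. In section 12.1, add that log lactate is analysed in the planned mixed model with log D1 lactate as covariate, and that results are reported as geometric mean ratios with 95% confidence intervals. Clearance can stay as a descriptive measure, with its formula stated.

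The cost is a few lines of text. The daily lactate values are the same ones clearance needs, so nothing is added for patients. The drawback is that a ratio of lactate levels is less familiar at the bedside than clearance.

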4.2.4 Randomisation

The randomization list will be computer-generated and stratified according to each ICU.

Patients will be randomly assigned in a 1:1 ratio to FX06 or standard of care.

Concealment of the study-group assignments is achieved with the use of a centralized, secure, interactive, Web-based response system (CleanWeb, Telemedicine Technologies) accessible from each study center.

After each randomization, a treatment number is allocated to the patient and a confirmation email of randomization is sent automatically to the investigator concerned and the URC.

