5.2 Follow-up visits

5.2.1 D2 to D5 (all data recorded at 10 O’Clock in the morning)

- Vital status
 - Weight of the patient
 - Daily fluid balance
 - Co-infection or not
 - Specific treatment received for SARS-CoV-2 (CTC, Remdesivir)
 - Diuretics
 - RRT or not
 - Ongoing prone-positioning (prone positioning on the day on the evaluation)
 - Standard clinical monitoring (arterial pressure, heart rate)
 - Ventilatory settings:
 - VV-ECMO Y/N
 - Ventilatory mode (ACV, PSV, APRV, spontaneous breathing)
 - Tidal volume
 - Respiratory rate
 - Positive end-expiratory pressure (PEEP)
 - Plateau pressure
 - FiO₂
 - Level of catecholamines: inotrope score, calculated as IS= dose of dobutamine (µg/kg/min)+
-

- 100 x [dose of norepinephrine ($\mu\text{g}/\text{kg}/\text{min}$) + dose of epinephrine ($\mu\text{g}/\text{kg}/\text{min}$)] [16]
 - Supplementation by hydrocortisone Y/N
 - Biological exams:
 - o Arterial blood gases
 - o Haematology (blood count)
 - o Ionogram, renal and hepatic markers
 - o serum glucose, CRP, LDH, NT-pro-BNP, procalcitonin, troponin
 - o Coagulation tests: PT ratio, aPTT, fibrinogenemia, D-Dimers
 - o Albuminemia
 - ECG
 - Use of renal replacement therapy
 - SOFA score
 - Chest x-ray
 - Trans-thoracic echocardiography
- Assessment of transpulmonary thermodilution (TPT) parameters. **Two measurements will be made, one before administration of the treatment, and one 3 hours after at day 2 [7].** For day 3 to D5, one measurement will be made before administration of the treatment. **All parameters will be evaluated in supine position. Parameters recorded will be: Extra-vascular lung water index, Global end-diastolic volume index, pulmonary vascular permeability index, and cardiac index.** Central venous and arterial lines used for the routine care of the patient will be compatible with TPT systems (either PICCO, Getinge, Germany or EV1000, Edwards Lifesciences, US).
 - Treatment
 - Administration by IV perfusion (400mg FX06 intravenously or placebo as a two-time bolus within 10 minutes interval)

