12.5 Method for taking into account missing, unused or invalid data

Missing data will be described.

No replacement of missing patients is planned. Dealing with very severe patients hospitalized in ICU, we anticipate no loss of follow up.

12.6 Management of modifications made to the analysis plan for the initial strategy.

Any changes made to the statistical analysis plan must be justified and will be done before the beginning of the statistical analysis.

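### The primary PD endpoint cuts the 3-hour EVLWi change at more than 30% without justification; a moderate acute effect or concentration-response relation may be missed.

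*Protocol*

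**What the plan says.** Protocol section 4.1.2, repeated in the Summary, describes a PK/PD analysis based on the FX06 concentrations, "with a reduction of EVLWi of more than 30% before and 3 hours after injection as primary PD endpoint at day 2". Section 5.2.1 schedules the readings this needs: "Two measurements will be made, one before administration of the treatment, and one 3 hours after at day 2". On days 3 to 5 there is only a pre-dose reading.

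The figure of 30% appears in two other places. Section 12.2 sizes the trial on "a 30% decrease in EVLWi in FX06 treated patients compared to controls at Day 7". Section 3.2 defines an exploratory responder by a change of more than 30% between D1 and D7.

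Section 12.1 analyses EVLWi as a continuous variable by ANCOVA on the D1 to D7 change and by a mixed model over 7 days. Neither names the 3-hour change. For other binary efficacy outcomes the section lists a chi-squared or Fisher test.

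Concentrations are sampled around the day-1 dose (sections 5.1, 5.6 and 5.7). Section 5.1 also allows sampling every other day from D1 to D5.

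**The concern.** The protocol itself fixes the form, cut, window and day of this endpoint, so it is a stated choice and not a detail left to a later analysis plan. Nothing in the document supports a 30% threshold over 3 hours. The only other uses of 30% refer to the whole week.

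A patient whose EVLWi falls by 25% counts the same as one with no change, although both readings are in hand. If the typical acute fall is well short of 30%, few treated patients cross the line. The analysis then has little ability to show an acute drug effect or to relate that effect to concentration. The pre-dose to 3-hour contrast is the only stated use of the extra day-2 reading, and no other named analysis recovers it.

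**Working it through.** **Inputs from the protocol.** Section 12.2: "standard deviation for EVLWi during ARDS is around 5 ml/kg predicted body weight"; "Assuming a baseline mean of EVLWi of 13.4"; effect "a 30% decrease in EVLWi in FX06 treated patients compared to controls at Day 7"; "for 80% power and an overall 5% two-sided" alpha. Section 4.2.4: 1:1 allocation. Section 12.5: "we anticipate no loss of follow up".

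**The plan's own figure.** The effect is 0.30 × 13.4 = 4.02 ml/kg. Then n = 2 × [5 × (1.960 + 0.842) / 4.02]² = 24.28, which rounds up to the stated 25 per group. The sample size reproduces (t-test power at 25 per group is 79.5%).

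**Assumptions for the 3-hour change.** The protocol gives neither a mean nor an SD. I take the percentage fall as normal, with mean 0 on placebo, mean μ on FX06 and SD s = 10, 15 or 20%. As a rough guide to that range, a cross-sectional SD of 5 and a correlation ρ between the two readings give a change SD of 5√(2(1−ρ)). As a percentage of 13.4 this is 11.8% at ρ = 0.95, 16.7% at ρ = 0.90 and 23.6% at ρ = 0.80.

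**Formulas.** The responder probability is 1 − Φ((30 − μ)/s). For s = 15 and μ = 10 it is 1 − Φ(1.33) = 9.1% on FX06 and 1 − Φ(2) = 2.3% on placebo. Power for the cut is the exact probability that Fisher's test gives p ≤ 0.05 at 25 per arm. Power for the continuous change is that of a two-sample t test with noncentrality (μ/s)√(25/2), which is 2.36 in the same example.

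| SD | True mean fall | Expected responders of 25, FX06 / placebo | Power, continuous | Power, >30% cut (Fisher) |
|---|---|---|---|---|
| 10% | 10% | 0.6 / 0.03 | 93% | 0% |
| 10% | 15% | 1.7 / 0.03 | >99% | 0.5% |
| 10% | 20% | 4.0 / 0.03 | >99% | 19% |
| 10% | 30% | 12.5 / 0.03 | >99% | >99% |
| 15% | 10% | 2.3 / 0.6 | 64% | 1% |
| 15% | 15% | 4.0 / 0.6 | 93% | 14% |
| 15% | 20% | 6.3 / 0.6 | >99% | 52% |
| 15% | 30% | 12.5 / 0.6 | >99% | 99% |
| 20% | 10% | 4.0 / 1.7 | 41% | 7% |
| 20% | 15% | 5.7 / 1.7 | 74% | 22% |
| 20% | 20% | 7.7 / 1.7 | 93% | 49% |
| 20% | 30% | 12.5 / 1.7 | >99% | 92% |

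With no placebo responders, Fisher's test needs 6 FX06 responders of 25, because 5 against 0 gives p = 0.0502. A chi-squared approximation is more favourable to the cut (10 to 38% for mean falls of 10 to 15%), but it is unreliable at these expected counts and still falls short of the continuous analysis.

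**Wider SD.** At s = 25% and true falls of 10, 15, 20 and 30%, continuous power is 28, 55, 79 and 99%. With the cut it is 8, 19, 36 and 79%.

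**Concentration-response.** This was simulated within 25 active patients, with an assumed correlation of 0.5 between concentration and fall. Power is about 75% when the fall is kept continuous. Comparing concentrations between responders and non-responders gives 3, 20 and 32% (SD 10, 15, 20%) at a mean fall of 10%, and 14, 32 and 39% at 15%. Over mean falls of 10 to 30% the range is roughly 3 to 54%, so here the cut loses power even when the mean fall equals the threshold.

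**The case against.** The strongest reply is that the result depends on an effect the protocol does not state. Section 5.2.1 cites a source for the day-2 measurements that cannot be consulted here, so a large 3-hour fall cannot be ruled out. If the true mean fall is near 30%, the cut detects the difference between arms. This stands, and the conclusion has to be conditional.

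A reader might infer that the PD endpoint demands in 3 hours the same effect the trial was sized on for a week. The percentages match but the contrasts do not: one is a within-patient change, the other a between-arm difference at Day 7. The match shows only that 30% was not justified separately for the short window.

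A reader might also infer that a working drug will be declared inactive, or that the choice of dose hangs on this result. The documents support neither. EVLWi stays continuous in the primary ANCOVA and in the mixed model, both day-2 readings are recorded, and the trial studies a single daily dose with no dose-selection objective.

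The between-arm power figures can be criticised because PK/PD concerns concentration and response, and section 12.1 does not expressly assign Fisher's test to this endpoint. The concentration-response calculation meets that point, and the loss remains. Finally, a high cut does limit false responders from noise: at most 1.7 of 25 are expected on placebo for SDs up to 20%. That is true, but it does not restore the power lost.

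**Conclusion.** The point holds in a conditional form. The >30% cut over 3 hours is unjustified in the protocol, and dichotomising may hide a moderate acute effect or a concentration-response relation. With an assumed SD of 10 to 20%, a placebo mean of 0 and 25 per arm, power for a true 10 to 15% fall is 41 to >99% continuous against 0 to 22% with the cut. For a true 20% fall it is 93 to >99% against 19 to 52%. At a true 30% fall both detect the between-arm difference (>99% against 92 to >99%). For the concentration link, at an assumed correlation of 0.5, it is about 75% against roughly 3 to 54%.

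The SD, the mean fall and the correlation are all assumptions. The effect is confined to one secondary PK/PD endpoint; the primary analysis is untouched. The change is worth making because it improves sensitivity without any further EVLWi measurement.

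**What to change.** In section 4.1.2 and the Summary, define the primary PD endpoint as the continuous change in EVLWi from the pre-dose to the 3-hour reading on D2, as a log ratio or percentage change. Compare it between arms with adjustment for the pre-dose value, and relate it as a continuous variable to FX06 concentration in the active arm. Report the proportion with a fall of more than 30% descriptively. This costs wording only, since the same two readings are used.

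Separately, reconcile the PK and PD days. Concentrations are scheduled on D1, or optionally every other day from D1 to D5, while the PD reading is on D2. Sampling on D1, D3 and D5 would still leave D2 without a concentration. Until the schedule and the PK/PD text agree, even a continuous D2 change would be paired with another day's concentrations. That step may need a change to the sampling schedule as well as to the text.
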